5.2.5 Other safety parameters

Assessment of disease state:

will be used to evaluate the disease severity. Refer to Section 5.2. In addition investigator may use CGI-S and his/her clinical judgment for assessing schizophrenia worsening/ relapse.

Schizophrenia worsening (i.e., deterioration of chronic residual symptoms): Fluctuation in the severity of symptoms is common and should be managed and reported as per the clinical judgment of the investigator. Adjustment of background medication is allowed when necessary. In such cases, schizophrenia worsening must be reported as AE per the clinical judgment of the investigator.

Schizophrenia Relapse (acute episode): If severity of schizophrenia symptoms fulfils the criteria of relapse (acute episode), investigator must report relapse as AE. Definition of relapse for this program is: Increased level of care (such as hospitalization, home hospitalization, emergency room (ER) visit due to psychotic symptoms) due to worsening of psychotic symptoms / increased per investigators judgment.

Page 59 of 112

Proprietary confidential information © 2023 Boehringer Ingelheim International GmbH or one or more of its affiliated companies

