7. STATISTICAL METHODS AND DETERMINATION OF SAMPLE SIZE

The primary efficacy objective is to assess the absolute difference in adjusted mean change from baseline to Week 26 in MCCB overall composite T-score (cognition) for once daily oral treatment with Iclepertin 10mg QD as compared with placebo in patients with CIAS. The key secondary efficacy objectives are to assess the absolute difference in adjusted mean change from baseline to Week 26 in SCoRS interviewer total score and adjusted total time T-score in VRFCAT between Iclepertin 10mg QD and placebo. Intercurrent events will be addressed using a strategy that differs depending upon the nature of the intercurrent event.

The treatment effect for the following treatment policy is of interest: patients remain on randomized treatment for the duration of the trial unless an exacerbation or acute episode or an event considered to be drug-related interrupts or discontinues treatment. Changes in background medication or non-pharmacological intervention are allowed.

Estimation will assume that the policy is followed by all randomized patients. All measurements obtained for patients while on this policy are therefore relevant for the estimation of the primary estimand, while measurements obtained after a deviation from this policy are not relevant for the estimation of the primary estimand.

The following intercurrent events are considered to form part of the treatment policy being assessed and hence subsequent measurements are included in the primary analysis of the endpoint:

- Change in background medication (e.g. antipsychotics, etc.)
- Change in non-pharmacological therapy (e.g. cognitive therapy, any kind of psychotherapy, nicotine withdrawal therapy, diet, etc.)
- Exacerbation or acute episode which results in interruption or early termination of treatment
- Investigator assessed drug-related AEs which lead to early termination of study medication
- Protocol-defined drug withdrawal due to treatment, e.g. haemoglobin decrease, concomitant medications with CYP3A4 substrates
- Change in study partner in the assessment of functional capacity, e.g. SCoRS.

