#### 6.3 INTERCURRENT EVENTS

Definition and technical specification of protocol defined intercurrent events (ICEs) are listed in Table 6.3: 1. In general, when handled under the hypothetical approach, data collected during the off-treatment period of an ICE will be considered irrelevant to the estimand and excluded from the analysis. While off-treatment data will be excluded, the patient will still be

considered as on-treatment (hypothetically) from an analysis perspective by the statistical models, and during any imputations.

For an ICE of temporary treatment discontinuation or interruptions, the off-treatment period spans from the last treatment administration prior to the interruption + REP to the restart of the study medication. For an ICE of early permanent treatment discontinuation, the off-treatment period starts from the last treatment administration + REP. Figure 6.3: 1 illustrates the on-/off-treatment status after each type of ICEs. When there is more than one ICE of early permanent treatment discontinuation, any treatment policy ICE take precedence in data and analysis handling over any hypothetical ICE.

ICEs of change in concomitant therapies and other ICEs will always be considered as part of the treatment policy in the primary and all supplementary estimands. ICEs of this category will not affect the on-/off- treatment status which is only determined by changes in the study medication. These ICEs will be listed and summarized descriptively but will not be explicitly accounted for in the inferential analysis of efficacy.

Table 6.3: 1 Definition and technical specification of intercurrent events

[figure not shown]
Type of Intercurrent Event	Definition and Documentary Sources	Handling under the Primary Estimand
Temporary Tr	reatment Discontinuations or Interruption	ons
Exacerbation or acute episode of schizophrenia resulting in interruption of treatment	Identified from data collected in the Temporary Trial Treatment Discontinuation and Adverse Event pages of the CRF:  - Temporary discontinuation of trial treatment reported with reason being "Adverse Event", and  - AE category reported as "Schizophrenia Relapse" or MedDRA preferred term coded as "Schizophrenia"	Treatment policy

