Temporary treatment discontinuation or interruption due to other reasons	Identified from data collected in the Temporary Discontinuation page of the CRF.	Hypothetical – only data collected from the end of REP after the interruption, to end of the interruption will be subject to exclusion from the analysis
Temporary treatment-switch	Identified from the dispensation records. Temporary treatment-switch will be handled as temporary interruptions in the same way for	Hypothetical – only data collected from the end of REP after the treatment switch, to end of the

due to dispensation error	both directions (iclepertin to placebo or placebo to iclepertin)	treatment switch will be subject to exclusion from the analysis			
Early Perman	Early Permanent Treatment Discontinuation				
Exacerbation or acute episode of schizophrenia resulting in early termination of treatment	Identified from data collected in the Adverse Event page of the CRF:  - "Drug Withdrawn" reported in the Action Taken with Study Treatment field, and  - Category reported as "Schizophrenia Relapse" or MedDRA preferred term coded as	Treatment policy			
Investigator assessed drug- related adverse events which lead to early termination	"Schizophrenia"  Identified from data collected in the Adverse Event page of the CRF:  - "Drug Withdrawn" reported in the Action Taken with Study Treatment field, and	Treatment policy			
of study medication	- "Yes" reported in the Relationship to Study Treatment field				
Protocol-defined drug withdrawal due to treatment – haemoglobin decrease	Identified from data collected in the End of Treatment and Adverse Event pages of the CRF and laboratory data:  - Subject who did not complete the planned treatment period as reported in the End of Treatment page with reason being "Adverse Event", and  - AE indicating haemoglobin decrease with action taken being "Drug Withdrawn"	Treatment policy			
Protocol-defined drug withdrawal due to treatment – CYP3A4 inhibitors or CYP3A4 sensitive drugs with NTI	Identified from data collected in the End of Treatment page of the CRF:  - Subject who did not complete the planned treatment period as reported in the End of Treatment page with "Protocol Deviation" as the reason, and  - Use of CYP3A4 inhibitors or CYP3A4 sensitive drugs with	Treatment policy			

	NTI specified as the detailed reason of discontinuation	
Early termination of study	Identified from data collected in the End of Treatment page of the CRF:	Hypothetical

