medication due to other AEs	- Subject who did not complete the planned treatment period as reported in the End of Treatment page with reason being "Adverse Event" and not otherwise covered by any of the ICEs above.	
Early termination of study medication due to perceived lack of	Identified from data collected in the End of Treatment page of the CRF:  - Subject who did not complete the planned treatment period as	Hypothetical
efficacy	reported in the End of Treatment page with reason being "Perceived Lack of Efficacy".	
Early termination of study	Identified from data collected in the End of Treatment page of the CRF:	Hypothetical
medication due to other reasons	- Subject who did not complete the planned treatment period as reported in the End of Treatment page for reasons not covered by any of the ICEs above.	
Change in Co	ncomitant Therapies and Other ICEs	
Change in background medication	Identified from data collected in the Concomitant Medications page of the CRF:  - Start of a new or stop of an ongoing antipsychotic, benzodiazepines (or derivatives),	Treatment policy
	anticholinergics, antiepileptics, or antidepressants during the on- treatment period, or	
	- Change of dosage or dosing frequencies of an on-going antipsychotic, benzodiazepines (or derivatives), anticholinergics, antiepileptics, or antidepressants during the on-treatment period	
	See Table 10.7: 1 for definitions of antipsychotics, benzodiazepines (or	

	derivatives), anticholinergics, antiepileptics, and antidepressants.	
Change in psychotherapy	Identified from data collected in the Psychotherapy page of the CRF:	Treatment policy
	- Change in frequency, setting or session of a psychotherapy during the on-treatment period	
Change in other non-pharmacological	Identified from data collected in the Concomitant Non-Drug Therapies page of the CRF:	Treatment policy
therapy	- Start of a new non-drug therapy or stop of an on-going non-drug therapy during the on-treatment period	
Change in study partner in the assessment of functional capacity,	Identified from data collected in the Study Partner Informed Consent page of the CRF and date/time of SCoRS assessments:	Treatment policy – relevant only to endpoints from the SCoRS assessment
e.g. SCoRS	- Any new study partner informed consent signed between the baseline SCoRS assessment and the SCoRS assessment being considered	

Figure 6.3: 1 On-/off-treatment status of the study medication for efficacy analysis after ICEs

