# AEs suggestive of abuse potential or related to CNS depressant effects

In support of an evaluation of human abuse potential, user-defined AE categories (UDAEC) are defined in Table 7.8.1: 1 for AEs suggestive of abuse potential and AEs related to CNS depressant effects.

Table 7.8.1: 1 MedDRA preferred terms for user-defined AE categories of AEs suggestive of abuse potential or related to CNS depressant effects

User-defined AE category	MedDRA preferred terms	
Drug abuse, dependence,	Accidental death	Intentional overdose
withdrawal and substance- related disorders, including	Drug abuse	Muscle rigidity
diversion	Accidental overdose	Nasal necrosis
	Accidental poisoning	Nasal septum perforation
	Dependence	Nasal septum ulceration
	Drug abuser	Needle track marks
	Product administered at inappropriate site	Neonatal complications of substance abuse
	Drug dependence	Overdose
	Drug detoxification	Poisoning
	Drug dependence antepartum	Poisoning deliberate
	Drug dependence, postpartum	Substance dependence
	Drug diversion	Prescription form tampering
	Drug tolerance	Product tampering
	Drug tolerance increased	Product used for unknown indication
	Toxicity to various agents	Rebound effect
	Drug use disorder	Seizure
	Drug use disorder antepartum	Status epilepticus
	Drug use disorder, postpartum	Substance abuse
	Drug withdrawal convulsions	Substance abuser
	Drug withdrawal headache	Substance use
	Drug withdrawal syndrome	Substance use disorder
	Drug withdrawal syndrome neonatal	Substance-induced mood disorder
	Generalised tonic-clonic seizure	Substance-induced psychotic disorder

	Hangover	Treatment noncompliance
	Intentional product misuse	Withdrawal syndrome
Euphoria-related adverse	Dizziness	Feeling drunk
events	Euphoric mood	Feeling of relaxation
	Feeling abnormal	Inappropriate affect
CNS depressant effects	Depressed level of consciousness	Sedation
	Fatigue	Sluggishness
	Hypersomnia	Somnolence
	Lethargy	Stupor
	Loss of consciousness	
Stimulation and anxiety-	Agitation	Morbid thoughts
related adverse events	Anxiety	Nervousness
	Anxiety disorder	Panic attack
	Anticipatory anxiety	Panic disorder
	Energy increased	Panic reaction
	Fear	Psychogenic tremor
	Fear of death	Psychomotor hyperactivity
	Feeling jittery	Restlessness
	Generalised anxiety disorder	Tension
	Hypervigilance	
Perceptual disturbances /	Abnormal dreams	Hypoaesthesia
psychotomimetic effects	Acute psychosis	Ideas of reference
	Aggression	Illogical thinking
	Alice in wonderland syndrome	Illusion

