	Altered state of consciousness	Incoherent
	Altered visual depth perception	Indifference
	Anger	Jamais vu
	Communication disorder	Loose associations
	Confusional state	Magical thinking
	Consciousness fluctuating	Nightmare
	Déjà vu	Paranoia
	Delirium	Paroxysmal perceptual alteration
	Delusion	Psychotic behaviour
	Delusion of grandeur	Psychotic disorder
	Delusion of reference	Psychotic symptom
	Delusion of replacement	Reactive psychosis
	Delusional perception	Rebound psychosis
	Derailment	Sensory disturbance
	Disinhibition	Sensory level abnormal
	Disorientation	Slow speech
	Dysarthria	Somatic delusion
	Flight of ideas	Somatic hallucination

	Formication	Staring
	Hallucination	Suspiciousness
	Hallucination, auditory	Tangentiality
	Hallucination, gustatory	Thinking abnormal
	Hallucination, olfactory	Thought blocking
	Hallucination, synaesthetic	Thought broadcasting
	Hallucination, tactile	Thought insertion
	Hallucination, visual	Thought withdrawal
	Hallucinations, mixed	Transient psychosis
	Hostility	
Dissociation	Daydreaming	Hypogeusia
	Depersonalisation/derealisation disorder	Metamorphopsia
	Derealisation	Ocular discomfort
	Diplopia	Oral dysaesthesia
	Dissociation	Oral hyperaesthesia
	Dissociative disorder	Pain threshold decreased
	Dissociative identity disorder	Paraesthesia
	Dysaesthesia	Paraesthesia oral
	Dysaesthesia pharynx	Pharyngeal hypoaesthesia
	Dysgeusia	Pharyngeal paraesthesia
	Dysmetropsia	Photophobia
	Feeling cold	Photopsia
	Feeling hot	Synaesthesia
	Feeling of body temperature change	Time perception altered
	Flashback	Tinnitus
	Hyperacusis	Vision blurred
	Hyperaesthesia	Visual impairment
	Hypersensitivity	
Mood disorders and	Abnormal behaviour	Depressive delusion
disturbances	Affect lability	Depressive symptom
	Affective disorder	Disturbance in social behaviour
	Anhedonia	Emotional disorder
	Antisocial behaviour	Emotional distress
	Apathy	Feeling of despair
	Asocial behaviour	Flat affect
	Attention-seeking behaviour	Hypomania
	Belligerence	Impatience
	Blunted affect	Impulse-control disorder
	Compulsive cheek biting	Impulsive behaviour
	Compulsive handwashing	Irritability
	Compulsive hoarding	Mania

	Compulsive lip biting	Mood altered	
	Compulsive sexual behaviour	Mood swings	
	Compulsive shopping	Parasomnia	
	Obsessive-compulsive symptom	Personality change	
	Compulsions	Sleep talking	
	Confusional arousal	Sleep terror	
	Depressed mood	Sleep-related eating disorder	
	Depression	Somnambulism	
Mental and cognitive	Amnesia	Impaired driving ability	

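### SAP Table 6.3: 1 can send a psychotic exacerbation to the hypothetical strategy when it is not flagged as relapse and is coded to a term other than Schizophrenia

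*SAP*

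**What the plan says.** Protocol section 7 lists the events that belong to the treatment policy, so that later measurements stay in the primary analysis. One of them is "Exacerbation or acute episode which results in interruption or early termination of treatment". No coding condition is attached. The examples it gives of events that break the policy are administrative or somatic; none is psychiatric.

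Protocol section 5.2.5 separates two things. Relapse, equated with an acute episode, is defined by "Increased level of care (such as hospitalization, home hospitalization, emergency room (ER) visit due to psychotic symptoms" and must be reported as an AE; part of that definition is blacked out. Schizophrenia worsening below that level is described separately, and it too is reported as an AE when background medication is adjusted. The word exacerbation is not defined.

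SAP Table 6.3: 1 uses the protocol's own label for the event but adds an identification rule. The interruption row requires "AE category reported as 'Schizophrenia Relapse' or MedDRA preferred term coded as 'Schizophrenia". The permanent-stop row repeats it: "Category reported as 'Schizophrenia Relapse' or MedDRA preferred term coded as" Schizophrenia. A separate row keeps a permanent stop under treatment policy if the investigator judged the AE drug-related, and treatment policy takes precedence where a permanent stop meets both kinds of row. Remaining AE stops, with "reason being 'Adverse Event' and not otherwise covered by any of the ICEs above", are hypothetical. So are interruptions for any other reason.

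**The concern.** The SAP foresees psychotic events under other preferred terms. Table 7.8.1: 1, built for abuse potential, lists "Acute psychosis" and "Psychotic symptom" alongside Psychotic disorder, hallucination and delusion terms and Paranoia. None of these is mapped to the exacerbation rows. Two patients with the same clinical event could therefore be handled in opposite ways because one site's wording was coded to Schizophrenia and another's was not. One keeps the post-event data. The other has them excluded and is modelled as though still on treatment. At stake is whether the primary analysis estimates the effect that protocol section 7 describes.

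**Working it through.** **1. Route each case through Table 6.3: 1.**

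| Event | Row reached | Handling |
|---|---|---|
| Stop or interruption, relapse category ticked, any preferred term | Exacerbation | Treatment policy |
| Stop or interruption, preferred term Schizophrenia | Exacerbation | Treatment policy |
| Permanent stop, other term, no relapse flag, judged drug-related | Drug-related AE | Treatment policy |
| Permanent stop, other term, no relapse flag, not judged drug-related | Other AEs | Hypothetical |
| Interruption, other term, no relapse flag, related or not | Other reasons | Hypothetical |

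The gap is the last two rows. The drug-related route does not exist for interruptions.

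**2. What is excluded.** The off-treatment period starts at last dose + 12 days (SAP sections 6.1 and 6.3).
- The early end-of-treatment visit, which includes the MCCB, is due within 7 days of the last dose (protocol section 6.2.3.4). Since 7 < 12, that MCCB is kept unless it falls within 28 days of the previous one (SAP section 5.1).
- If it is done before Day 127 it maps to Week 12 (Table 6.7: 1). The excluded value is then the later Week 26 assessment, which is the primary time point. From Day 127 it is eligible for Week 26.
- A Tower of London score from any day after Day 1 is eligible for Week 26 (Table 6.7: 3).
- An interruption loses data only between the end of the 12 days and the restart. The MCCB is scheduled after baseline only at Weeks 12 and 26 and at early end of treatment, so a scheduled score is lost only if the pause exceeds 12 days and spans one of those visits.

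**3. Reproduce the plan's power (protocol section 7.5).** With d = 0.35, n = 220 per arm and one-sided alpha 0.025, the noncentrality of the two-sample t-test is d × √(n/2) = 0.35 × √110 = 3.67. Power is 95.6%, against 95% stated in the text and 95.6% in Table 7.5: 1.

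**4. Size of the gap.** From protocol section 7.5: 586 randomised, 30% to 40% stopping early, and 25% to 50% of those with later efficacy data.
- Stops: 586 × 0.30 = 176 to 586 × 0.40 = 234.
- Stops with later data: 176 × 0.25 = 44 to 234 × 0.50 = 117.

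The share f of stops that falls in the gap is not in the documents. Taking f as an assumption:

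| Assumed f | Stops misrouted | With later data | Share of 586, upper end |
|---|---|---|---|
| 1% | 1.8 to 2.3 | 0.4 to 1.2 | 0.2% |
| 5% | 8.8 to 11.7 | 2.2 to 5.9 | 1.0% |
| 10% | 17.6 to 23.4 | 4.4 to 11.7 | 2.0% |

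These counts cover permanent stops; the documents project no number of interruptions.

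**5. Power in the worst row.** Removing 11.7 patients, half from each arm, leaves 220 − 5.9 = 214.1 per arm. The noncentrality is 0.35 × √(214.1/2) = 3.62 and power is 95.1%.

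**The case against.** The strongest reply is that no contradiction has been shown. Exacerbation is undefined, and the protocol's eligibility footnotes use the word for escalation of care. Section 5.2.5 calls fluctuation of residual symptoms common and keeps it apart from relapse. The blacked-out words may also widen the relapse definition. If exacerbation means relapse, the CRF category catches it under any preferred term, and drug-related permanent stops have their own route. Protocol section 7.2.2 also plans a supplementary analysis with every intercurrent event under treatment policy, which keeps all the observations at issue. Parts of the SAP are not public.

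Much of this stands. A reader might infer that every psychotic stop not coded Schizophrenia loses all its later MCCB scores. The documents do not support that: flagged relapses and drug-related permanent stops are retained, and the early end-of-treatment score normally is too. A reader might also infer that the rule favours one arm. No rate by arm is given, so the direction cannot be stated.

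Two things remain. Protocol section 7 names exacerbation and acute episode as alternatives, and the SAP itself did not rely on the relapse flag alone; it added a preferred-term route, but one that is a single term wide. An unflagged event coded Acute psychosis fits the row's label and misses its rule. The supplementary analysis changes the handling of all events at once, so it neither isolates nor repairs this misrouting in the primary analysis.

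The objection to importing the whole abuse-potential list is also sound. Its symptom terms could bring in the residual-symptom fluctuation that the protocol distinguishes from relapse.

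**Conclusion.** The concern holds in a narrow form. The identification rule in Table 6.3: 1 is tighter than the event that protocol section 7 places under treatment policy. Events that are unflagged, coded to another term and, for permanent stops, not judged drug-related can therefore be handled against the stated estimand. How many sub-relapse events count as exacerbations is open, because the term is undefined.

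The number affected is not in the documents and is probably small: roughly 0 to 12 patients with later data if 1% to 10% of projected stops fall in the gap, at most 2% of those randomised. That range rests on an assumed share and on the protocol's own projections of stopping and retrieval. Power is essentially unaffected (95.1% or more, against 95.6%). The issue is alignment with the estimand, and it should be settled before treatment release, when the choice cannot look data-driven.

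**What to change.** In both exacerbation rows of Table 6.3: 1:
- Define exacerbation, and use the same definition in protocol and SAP.
- Add to Schizophrenia a short, closed list of psychotic-episode preferred terms, for example Acute psychosis and Psychotic disorder.
- Have all AE-related stops and interruptions with psychotic terms classified by blinded medical review before the treatment information is released (SAP section 8). Symptom-level terms (hallucination, delusion, paranoia) would count only when that review judges the event an exacerbation of schizophrenia.

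The cost is a wording change, one blinded listing review and a few borderline judgements. No new data collection is needed.

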1.2 DRUG PROFILE

Iclepertin is a glycine transporter 1 (GlyT1) inhibitor under development for treatment of CIAS. Iclepertin improved cognition in patients with schizophrenia in Phase II, achieving proof-of-clinical-concept.

Mode of action

Iclepertin is a potent and selective inhibitor of the Glycine Transporter 1 (GLYT1) and as such, increases the concentration of the NMDA receptor co-activator glycine in the synaptic cleft. In vivo proof-of-mechanism (i.e. indirect target engagement in the brain) was demonstrated by a dose-dependent increase of glycine in Cerebrospinal Fluid (CSF), both in rats [U13-2547] and humans [c03724403].

Enhancing glutamatergic neurotransmission is believed to improve brain plasticity (also referred to as neuroplasticity) which is essential for learning and memory. Indeed, pre-clinical studies with Iclepertin have demonstrated pro-cognitive properties in relevant animal models of learning and memory and Phase II results showed a beneficial effect on cognition that is known to be impaired in patients with schizophrenia. It is therefore expected that treatment with Iclepertin has the potential to improve cognition that was impaired by the schizophrenia illness.

Residual Effect Period

The Residual Effect Period (REP) of Iclepertin is defined as 12 days after the last dose of trial medication. This is the period after the last dose with measurable drug levels and/or pharmacodynamic effects still likely to be present.

Data from non-clinical and toxicology studies

In vivo target engagement in brain showed a dose-dependent increase of glycine in rat CSF, with a ~50% increase at CSF levels of Iclepertin of ~1x GLYT1 IC50 [U13-2547]. Exposure leading to this level of glycine increase is expected to produce clinical efficacy.

Iclepertin has been tested in a comprehensive package of safety pharmacology, genetic toxicology, fertility and early embryonic development, embryo-foetal development, and repeat-dose toxicology studies up to 39 weeks of dosing. Results of these studies support clinical trials in adults for chronic administration, including women of childbearing potential (WoCBP).

Iclepertin has two major human metabolites, M530 (BI 758790) and M232 (BI 761036). These metabolites do not show any relevant activity on GlyT1 and GlyT2, nor against other off-targets tested, nor did they show any pharmacological or toxicological activity.

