#### 6.4 SUBJECT SETS ANALYSED

The following patient analysis sets are defined:

- Screened Set (SS): includes all patients who signed informed consent and were screened for the trial with at least one screening procedure done at Visits 1 or 1a.
- Randomised Set (RS): includes all patients who signed informed consent and were randomised into the trial, regardless of whether a patient was treated with trial medication. Patients randomized in error and discontinued from the study before the start of trial medication will be excluded from the RS. Patients in RS will be analysed under the randomized trial medication. The RS will be used for efficacy analyses as well as demographics and baseline characteristics.
- Treated Set (TS): includes all patients who signed informed consent and were treated with at least one dose of the trial medication. Patients in TS will be analysed under the actual trial medication received at randomisation. The TS will be used for safety analyses.

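### The exclusion window for kit mix-ups fits iclepertin-to-placebo errors but can keep drug-exposed assessments as placebo data in the reverse error; few assessments are at risk

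*SAP*

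**What the plan says.** SAP Section 6.3, Table 6.3: 1, has a row for a temporary treatment switch caused by a dispensation error, handled under the hypothetical strategy. It reads "Temporary treatment-switch will be handled as temporary interruptions in the same way for", and the sentence continues "both directions (iclepertin to placebo or placebo to iclepertin". The handling column limits the exclusion to one window: "only data collected from the end of REP after the treatment switch, to end of the", continuing "treatment switch will be subject to exclusion from the analysis".

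The rule is borrowed from interruptions, for which Section 6.3 says "the off-treatment period spans from the last treatment administration prior to the interruption + REP to the restart of the study medication".

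Protocol Section 1.2 states that the REP "is defined as 12 days after the last dose of trial medication" and explains it: "This is the period after the last dose with measurable drug levels and/or pharmacodynamic effects still likely to be present". SAP Section 6.4 adds, for the efficacy set, "Patients in RS will be analysed under the randomized trial medication".

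**The concern.** The REP describes iclepertin that remains after dosing stops. Placebo leaves no residue, so the same window does different things in the two directions.

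- **Iclepertin patient given placebo.** Residual drug covers the first 12 days, and assigned drug resumes when the error is corrected. Excluding only the stretch between is coherent.
- **Placebo patient given iclepertin.** Exposure starts with the first wrong dose and, on the protocol's own definition, lasts for 12 days after the last one. The rule keeps both stretches.

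The hypothetical strategy is meant to estimate what would have happened on the assigned treatment. In the second case, assessments made under iclepertin could enter the placebo mean, including for the primary endpoint.

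**Working it through.** **Inputs.** REP is 12 days (Protocol 1.2; SAP 6.1). Visit days are 64 (Visit 5), 85 (Visit 6), 106 (Visit 7), 148 (Visit 9), 169 (Visit 10) and 183 (Visit 11), each ±3 days (Protocol flow chart). MCCB, SCoRS and VRFCAT are measured at Weeks 12 and 26, ToL at Week 26, PRECIS at Weeks 15 and 24, and all of them at early end of treatment. Protocol 7.5 gives 220 evaluable patients per arm, standardized effect 0.35 and one-sided alpha 0.025. The documents give no rate of dispensing errors, so the number of affected patients is assumed below.

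**Step 1: the plan's own power.** 0.35 × √(220/2) = 3.671; 3.671 − 1.960 = 1.711; Φ(1.711) = 95.6%. This agrees with the 95% in Protocol 7.5 and the 95.6% in Table 7.5: 1.

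**Step 2: calendar time under the rule, placebo to iclepertin.** For a switch of L days, exposed days = L + 12, excluded days = max(0, L − 12), and exposed days not excluded = min(L, 12) + 12.

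| L | Exposed | Excluded now | Exposed, not excluded |
|---|---|---|---|
| 14 | 26 | 2 | 24 |
| 21 | 33 | 9 | 24 |
| 28 | 40 | 16 | 24 |

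A switch shorter than 12 days excludes nothing. These are days, not data; what matters is whether an assessment falls in them.

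**Step 3: which assessments can fall there.**

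- *Week 12.* If a wrong kit is issued at Visit 5, or corrected at Visit 5, the gap to Visit 6 is 85 − 64 = 21 days, or 15 to 27 with windows. It is never 12 or less. The same 21-day gap protects PRECIS at Visit 7 (106 − 85) and Visit 10 (169 − 148).
- *Week 26.* Visit 10 to Visit 11 is 183 − 169 = 14 days, or 8 to 20 with windows. At 12 days or less, the Week 26 value is kept whether the wrong kit was issued or corrected at Visit 10. This occurs in 15 of the 7 × 7 = 49 combinations of window days. That is a count of combinations, not a probability.
- *Early end of treatment.* This visit is due within 7 days of the last dose (Protocol 6.2.3.4), so inside the REP if that dose came from a wrong kit. SAP Table 6.7: 1 maps MCCB from Day 127 onward to Week 26, and Table 6.7: 3 maps ToL from Day 2 onward to Week 26.
- *Unscheduled assessments, and switches that start or end between visits.* Two kits are issued per visit (Protocol 4.1.4), so a mid-interval switch is possible.
- *Day on which a wrong kit ends.* The SAP does not say whether a switch ends at the last wrong dose or at the return to the correct kit. Protocol 4.1.4 puts the last dose on the day before the end-of-treatment visit. If the switch ends at the last wrong dose, a Visit 11 assessment after a wrong Visit 10 kit falls one day outside the window and is kept, even at the nominal 14 days. A Week 12 assessment on the day a wrong Visit 5 kit is replaced raises the same question. The interruption rule ends at restart, but nothing restarts after Visit 10.

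**Step 4: upper bound on dilution.** Suppose k of 220 placebo patients have a kept Week 26 value that carries the full drug effect. The effect becomes 0.35 × (1 − k/220).

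| k (assumed) | Effect | Power |
|---|---|---|
| 0 | 0.350 | 95.6% |
| 1 | 0.348 | 95.5% |
| 3 | 0.345 | 95.2% |
| 6 | 0.340 | 94.6% |
| 11 | 0.332 | 93.7% |
| 22 | 0.315 | 91.0% |

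**The case against.** The strongest reply is that the asymmetry barely reaches the data. A reader might infer from the day counts that each mix-up puts 24 days of drug-exposed results into the placebo arm. The visit schedule does not support that: for a wrong kit taken over one ordinary 21-day interval, the Week 12 value lies beyond 12 days from both the switch and the switch-back, and the nominal Week 26 value is 14 days after Visit 10. Apart from the unsettled end-of-switch boundary, exposure needs a dispensing error together with a compressed final interval, an off-schedule assessment or a mid-interval switch. This part of the objection stands.

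A reader might also infer that the error always pulls the treatment contrast toward zero. That assumes iclepertin changes test performance within days. The protocol reports an effect after 12 weeks of treatment and shows none at such short exposure; residual drug is not the same as an effect on MCCB. This stands too.

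Two further arguments carry less weight. The symmetry is deliberate, and the SAP uses REP-based periods alike in both groups; but a residual allowance has no basis where the preceding treatment was placebo. Protocol 7.2.2 also plans a supplementary analysis that censors all data after any intercurrent event. As worded, it would remove both stretches, but it leaves the primary analysis unchanged.

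Finally, Figure 6.3: 1 and the important-protocol-deviation specification named in SAP 6.2 could not be seen. Either might add a rule, although the table text limits the exclusion to the stated window.

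**Conclusion.** On the visible text, the rule is wrong for one direction of error. For placebo to iclepertin, it keeps assessments from the first 12 days on the wrong kit and from the REP after the last wrong dose, and they are analysed under placebo. No visible text corrects this for the primary analysis.

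The practical weight is small. Even if every kept value carried the full assumed effect, one affected placebo patient would cost about 0.1 percentage points of power and three about 0.4. If iclepertin improves performance that early, the bias is toward no difference; if it does not, there is essentially none. Type I error is not inflated. The size rests on an assumed number of affected patients, since no error rate is given. This is a minor correction.

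**What to change.** Split the table row by direction.

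- **Iclepertin to placebo:** keep the current window.
- **Placebo to iclepertin:** exclude assessments from the first wrong dose to the last wrong dose plus REP (12 days). For a 21-day switch, the excluded span rises from 9 to 33 days and no exposed day is kept.

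Writing the second window in terms of doses also settles the end-of-switch question for that direction. State the end point explicitly for the other direction too, and check Figure 6.3: 1 and the protocol-deviation specification for consistency.

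The cost is one table row and one programming condition, to be settled before unblinding so that no decision is made about individual placebo values afterwards. The downside is that a few more placebo values become missing, and more in one arm than the other for the same kind of error. The MMRM already handles such values under missing at random.
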